Committee Id: 200 **Committee Name:** IRB Expedited Review

Schedule Id: 33574 **Schedule Date:** 04/15/2023

Review Comments:

Canine Behavioral Assessment & Research Questionnaire (short version)

[figure not shown]
SECTION 1: Excitability

INSTRUCTIONS: Some dogs show little reaction to exciting events, while others become highly excited at the slightest novelty. By circling a number on the following 5-point scales (0=Calm, 4=Extremely excitable), please indicate your own dog's recent tendency to become excitable in the following circumstances (**please circle only one number**):

1. Just before being taken for a walk.

	Mild—Moderate excitability	
Calm: little or no special reaction	0.....1.....2.....3.....4	Extremely excitable: over-reacts, hard to calm down.

2. Just before being taken on a car trip.

	Mild—Moderate excitability	
Calm: little or no special reaction	0.....1.....2.....3.....4	Extremely excitable: over-reacts, hard to calm down.

SECTION 2: Aggression

INSTRUCTIONS: Most dogs display aggressive behavior from time to time—e.g. barking, growling, baring teeth, snapping, etc. By circling a number on the following 5-point scales (0= No aggression, 4= Serious aggression), please indicate your own dog's recent tendency to display aggressive behavior in each of the following circumstances (**please circle only one number**):

3. When approached directly by an unfamiliar **person** while being walked/exercised on a leash.

	Moderate aggression: growling/barking—baring teeth	
No aggression: No visible signs of aggression	0.....1.....2.....3.....4	Serious aggression: Snaps, bites or attempts to bite.

4. When toys, bones or other objects are taken away by a household member.

	Moderate aggression: growling/barking—baring teeth	
No aggression: No visible signs of aggression	0.....1.....2.....3.....4	Serious aggression: Snaps, bites or attempts to bite.

5. When approached directly by a household member while s/he (the dog) is eating.

	Moderate aggression: growling/barking—baring teeth	
No aggression: No visible signs of aggression	0.....1.....2.....3.....4	Serious aggression: Snaps, bites or attempts to bite.

6. When mailmen or other delivery workers approach your home.

No aggression:
No visible signs of aggression 0.....1.....2.....3.....4

Moderate aggression:
growling/barking—baring teeth

Serious aggression:
Snaps, bites or attempts to bite.

7. When his/her food is taken away by a household member.

No aggression:
No visible signs of aggression 0.....1.....2.....3.....4

Moderate aggression:
growling/barking—baring teeth

Serious aggression:
Snaps, bites or attempts to bite.

8. When approached directly by an unfamiliar **dog** while being walked/exercised on a leash.

No aggression:
No visible signs of aggression 0.....1.....2.....3.....4

Moderate aggression:
growling/barking—baring teeth

Serious aggression:
Snaps, bites or attempts to bite.

9. When strangers walk past your home when your dog is outside or in the yard.

No aggression:
No visible signs of aggression 0.....1.....2.....3.....4

Moderate aggression:
growling/barking—baring teeth

Serious aggression:
Snaps, bites or attempts to bite.

10. When barked, growled, or lunged at by another (unfamiliar) dog.

No aggression:
No visible signs of aggression 0.....1.....2.....3.....4

Moderate aggression:
growling/barking—baring teeth

Serious aggression:
Snaps, bites or attempts to bite.

11. When approached while eating by another (familiar) household **dog** (leave blank if no other dogs).

No aggression:
No visible signs of aggression 0.....1.....2.....3.....4

Moderate aggression:
growling/barking—baring teeth

Serious aggression:
Snaps, bites or attempts to bite.

12. When approached while playing with/chewing a favorite toy, bone, object, etc., by another (familiar) household **dog** (leave blank if no other dogs).

No aggression:
No visible signs of aggression 0.....1.....2.....3.....4

[figure not shown]
Moderate aggression:
growling/barking—baring teeth

Serious aggression:
Snaps, bites or attempts to bite.

SECTION 3: Fear and Anxiety

INSTRUCTIONS: Dogs often show signs of anxiety or fear when exposed to particular sounds, objects, persons or situations—e.g. crouching or cringing with tail tucked between the legs; whimpering or whining, freezing, trembling, or attempting to escape or hide. Using the following 5-point scales (0=No fear, 4=Extreme fear), please indicate your own dog's recent tendency to display fearful behavior in the following circumstances (**please circle only one number**):

13. When approached directly by an unfamiliar person while away from your home.

No fear/anxiety: No visible signs of fear	0.....1.....2.....3.....4	Mild—Moderate fear/anxiety	Extreme fear: cowers; retreats or hides, etc.
--	---------------------------	-----------------------------------	--

14. In response to sudden or loud noises (e.g. thunder, vacuum cleaner, car backfire, road drills, objects being dropped, etc.).

No fear/anxiety: No visible signs of fear	0.....1.....2.....3.....4	Mild—Moderate fear/anxiety	Extreme fear: cowers; retreats or hides, etc.
--	---------------------------	-----------------------------------	--

15. When an unfamiliar person tries to touch or pet the dog.

No fear/anxiety: No visible signs of fear	0.....1.....2.....3.....4	Mild—Moderate fear/anxiety	Extreme fear: cowers; retreats or hides, etc.
--	---------------------------	-----------------------------------	--

16. In response to strange or unfamiliar objects on or near the sidewalk (e.g. plastic trash bags, leaves, litter, flags flapping, etc.).

No fear/anxiety: No visible signs of fear	0.....1.....2.....3.....4	Mild—Moderate fear/anxiety	Extreme fear: cowers; retreats or hides, etc.
--	---------------------------	-----------------------------------	--

17. When approached directly by an unfamiliar dog.

No fear/anxiety: No visible signs of fear	0.....1.....2.....3.....4	Mild—Moderate fear/anxiety	Extreme fear: cowers; retreats or hides, etc.
--	---------------------------	-----------------------------------	--

18. When first exposed to unfamiliar situations (e.g. first car trip, first time in elevator, first visit to veterinarian, etc.).

No fear/anxiety: No visible signs of fear	0.....1.....2.....3.....4	Mild—Moderate fear/anxiety	Extreme fear: cowers; retreats or hides, etc.
--	---------------------------	-----------------------------------	--

19. When barked, growled, or lunged at by an unfamiliar dog.

No fear/anxiety: No visible signs of fear	0.....1.....2.....3.....4	Mild—Moderate fear/anxiety	Extreme fear: cowers; retreats or hides, etc.
--	---------------------------	-----------------------------------	--

20. When having nails clipped by a household member.

No fear/anxiety:
No visible signs
of fear

Mild—Moderate fear/anxiety

Extreme fear:
cowers; retreats or
hides, etc.

0.....1.....2.....3.....4

21. When groomed or bathed by a household member.

No fear/anxiety:
No visible signs
of fear

Mild—Moderate fear/anxiety

Extreme fear:
cowers; retreats or
hides, etc.

0.....1.....2.....3.....4

SECTION 4: Separation-related behavior.

INSTRUCTIONS: Some dogs show signs of anxiety when left alone, even for short periods of time. Thinking back over the recent past, how often has your dog shown each of the following signs of anxiety when left, or about to be left, on its own (**please check only one box per question**):

[figure not shown]
	Never	Seldom	Sometimes	Usually	Always
22. Restlessness/agitation/pacing.					
23. Barking or whining.					
24. Chewing/scratching at doors, floor, windows, curtains, etc.					

SECTION 5: Attachment and Attention-seeking.

INSTRUCTIONS: Most dogs are strongly attached to their people, and some demand a great deal of attention and affection from them. Thinking back over the recent past, how often has your dog shown each of the following signs of attachment or attention-seeking (**please check only one box per question**):

	Never	Seldom	Sometimes	Usually	Always
25. Tends to follow you (or other members of the household) about the house, from room to room.					
26. Tends to sit close to, or in contact with, you (or others) when you are sitting down					

SECTION 6: Training and obedience

INSTRUCTIONS: Some dogs are more obedient and trainable than others. By checking the appropriate boxes, please indicate how trainable or obedient your dog has been in each of the following situations in the recent past (**please check only one box per question**):

	Never	Seldom	Sometimes	Usually	Always
27. Obeys a "sit" command immediately.					
28. Obeys a "stay" command immediately.					
29. Easily distracted by interesting sights, sounds or smells.					

SECTION 7: Miscellaneous problems

INSTRUCTIONS: Dogs display a wide range of miscellaneous behavior problems in addition to those already covered by this questionnaire. Thinking back over the recent past, please indicate how often your dog has shown any of the following behaviors (**please check only one box per question**):

	Never	Seldom	Sometimes	Usually	Always
30. Chases or would chase birds, given the chance.					
31. Chases or would chase squirrels, rabbits, etc., given the chance.					
32. Escapes or would escape from home or yard, given the chance.					
33. Chews inappropriate objects.					
34. Pulls excessively hard when on the leash.					
35. Urinates against objects/ furnishings in your home.					
36. Urinates when left alone at night, or during the daytime.					
37. Defecates when left alone at night, or during the daytime.					

38. Hyperactive, restless, has trouble settling down.					
39. Playful, puppyish, boisterous.					
40. Active, energetic, always on the go.					
41. Chases own tail/hind end.					
42. Barks persistently when alarmed or excited.					

Thank you for providing this helpful information!

Positive and Negative Affect Schedule (PANAS-SF)

Indicate the extent you have felt this way over the past week.		Very slightly or not at all	A little	Moderately	Quite a bit	Extremely
PANAS 1	Interested	 1	 2	 3	 4	 5
PANAS 2	Distressed	 1	 2	 3	 4	 5
PANAS 3	Excited	 1	 2	 3	 4	 5
PANAS 4	Upset	 1	 2	 3	 4	 5
PANAS 5	Strong	 1	 2	 3	 4	 5
PANAS 6	Guilty	 1	 2	 3	 4	 5
PANAS 7	Scared	 1	 2	 3	 4	 5
PANAS 8	Hostile	 1	 2	 3	 4	 5
PANAS 9	Enthusiastic	 1	 2	 3	 4	 5
PANAS 10	Proud	 1	 2	 3	 4	 5
PANAS 11	Irritable	 1	 2	 3	 4	 5
PANAS 12	Alert	 1	 2	 3	 4	 5
PANAS 13	Ashamed	 1	 2	 3	 4	 5
PANAS 14	Inspired	 1	 2	 3	 4	 5
PANAS 15	Nervous	 1	 2	 3	 4	 5
PANAS 16	Determined	 1	 2	 3	 4	 5
PANAS 17	Attentive	 1	 2	 3	 4	 5
PANAS 18	Jittery	 1	 2	 3	 4	 5
PANAS 19	Active	 1	 2	 3	 4	 5
PANAS 20	Afraid	 1	 2	 3	 4	 5

Scoring:

Positive Affect Score: Add the scores on items 1, 3, 5, 9, 10, 12, 14, 16, 17, and 19. Scores can range from 10 – 50, with higher scores representing higher levels of positive affect.
Mean Scores: 33.3 (SD±7.2)

Negative Affect Score: Add the scores on items 2, 4, 6, 7, 8, 11, 13, 15, 18, and 20. Scores can range from 10 – 50, with lower scores representing lower levels of negative affect.
Mean Score: 17.4 (SD ± 6.2)

Your scores on the PANAS: Positive: _____ Negative: _____

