Cover Page for Clinical Trial Study

Official Title: The Effect of Animal-Assisted Therapy on Prosocial Behavior in Children with Developmental Delay or Autism Spectrum Disorder

NCT #: N/A

Date: November 11, 2024

Study Protocol

Clinical Study Description

The purpose of this study is to investigate the effect of animal-assisted therapy (AAT) on prosocial behavior and emotional regulation, both during and after AAT sessions, in children referred for an autism spectrum disorder (ASD) evaluation or documented developmental delay (DD) or behavioral concerns. We seek to address identified gaps in knowledge of the use of canines in therapy sessions by analyzing short- and long-term effects of AAT and human-animal interaction occurring in AAT sessions. Caregivers were given the option to enroll the child in the AAT study at the follow-up appointment after the diagnostic assessment was completed, or upon enrollment in the ASD program if the child had an ASD diagnosis. Each AAT study lasted between eight to 12 weeks, and caregivers had the option to re-enroll the child for the next study to continue addressing behavioral concerns. Animal-assisted therapy sessions lasted 30 to 45 minutes, depending on the age and ability of the participant. Sessions started with five to 10 minutes of free play with the canine, followed by sensory integration therapy based on the child's identified sensory profile. Participants then entered the clinic room for 20 to 30 minutes of a seated activity in which the therapist, a certified pediatric nurse practitioner (CPNP), taught coping and socialization strategies to participants and caregivers. Sessions concluded with five minutes of play with the canine. Play activities include fetch, soccer, hide and seek, and puzzles. The canine was trained to lay under the table in the clinic room while the therapist was working with the participants. He would provide grounding, light pressure, and deep pressure therapy if the participant became anxious during the sessions. The seated work was recorded using two cameras to ensure visibility of the interactions between the participant and therapist, canine, and caregiver; participant vocalizations and verbalizations; and participant facial expressions. We used two human-animal ethograms to code behavior during sessions and two behavioral assessments to note behavior occurring after sessions. All sessions occurred in the clinic located on the university's campus. Demographic data including participant age, gender, race, ethnicity, referral source, prior medical diagnoses, age of ASD or DD diagnosis, medications, and prior allied health, school, or psychological evaluations. The canine was trained as a therapy dog and was being trained as a service dog at the time of the study. The canine was present during sessions to interact with children and assist them to practice and develop skills to address identified deficits in social-emotional and adaptive functioning, prosocial behavior, and emotional regulation. AAT sessions were recorded to code interactions at a later time.

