
Objectives

1. Do interactions between a trained therapy canine and autistic children differ depending on the child's verbal abilities?
2. Is there a difference in prosocial behavior and emotional regulation in AAT sessions among children with varying verbal abilities?
3. Is there a difference in prosocial behavior and emotional regulation apart from animal-assisted therapy sessions among children with varying verbal abilities?

Design

We used standardized instruments to investigate human-animal intervention (HAI) occurring during AAT sessions and prosocial behavior and emotional regulation demonstrated by participants outside of AAT sessions. SPSS and Microsoft Excel were used to run the analysis. Descriptive statistics were utilized to compare prosocial behavior and emotional regulation occurring apart from AAT sessions between the two groups based on the self-report questionnaires completed by caregivers. Independent t-tests were used to analyze the differences in human-animal interaction among children with ASD with varying verbal abilities from the recorded sessions. The homogeneity of the variance (HOV) assumption between two groups was checked using Levene's test for equality of variances in SPSS program before conducting the t-tests analysis. Results of t-tests with adjusted degrees of freedom value were reported if the HOV was violated. The null hypothesis was set to reflect no significant difference in HAI between verbal and nonverbal groups for the independent t-tests; therefore, a significant difference in the human-animal interaction behaviors regarding the children's verbal abilities could be confirmed if the t-test results reject the null hypothesis. Cohen's d was used to report the effect sizes of the independent t-tests; values up to 0.20 were interpreted as small, 0.50 as medium, and 0.80 as large effect sizes.

Methods

Demographic data; past, family, and social histories; and prior therapy evaluations were collected during the initial consultation for enrollment into the ASD program.

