
The 3-AAT Observation ethogram, adapted with permission from Johns Hopkins University, was used to code both canine and human interaction during AAT sessions. The revised ethogram appraises the frequency of six domains of human interaction (affection, play, care, communication, comfort, withdrawal) and 24 subdomains of human behavior that can occur in an AAT session as seen in Table 1. The ethogram assesses the frequency, intensity, and duration of the interactions between the canine and child. Frequency is measured by a tally count and duration is assessed by rounding either up or down to the nearest 30 second mark. Each interaction has a code for intensity from 0 (not intense) to 3 (the most intense), and the mode of the interaction was entered to run the analysis.

The Strengths and Difficulties Questionnaire (SDQ) is a 25-item tool developed to assess five domains: Emotional Problems, Conduct Problems, Hyperactivity, Peer Problems, and Prosocial. The SDQ is the most used instrument in measuring therapeutic effect of interventions within the emotional state in children and adolescents ages 2 to 18 years, demonstrating reliable internal consistency and validity. The SDQ has two versions, one to be administered at the initiation of therapy and then a follow-up version that includes two additional questions examining the impact of the therapeutic intervention. Scores from four behavioral domains range from zero ("normal") to 10 ("very high concerns"), while Prosocial domain scores are reversed so that 10 indicates "normal" behavior and zero signifies "very high concerns". The SDQ also assesses the total, impact, internalizing, and externalizing scores to provide a complete overview of the child's behavior during the past four weeks. Total scores are the sum of the behavior domains except the Prosocial domains and range from zero (normal) to 40 (very high). Impact scores range from zero (normal) to 10 (very high) and reflect overall distress and impairment interfering with daily social interactions. Internalizing scores reflect the Emotional Problems and Peer Problems domains, while Externalizing scores are the sum of the Conduct Problems and Hyperactivity domains. Both the Internalizing and Externalizing domain scores range from zero (normal) to 20 (very high). The initial SDQ was administered at the beginning of the study and the follow-up assessment was used subsequently every four weeks until the study concluded.

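### Caregivers are said to complete the out-of-session questionnaires, but the only PANAS form supplied asks about the respondent's own feelings, so its scores cannot be securely read as the child's affect

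*Combined protocol and SAP*

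**What the plan says.** The third objective reads "Is there a difference in prosocial behavior and emotional regulation apart from animal-assisted therapy sessions among children with varying verbal abilities". The Design section and the Statistical Analysis Plan give the data source in the same words: a descriptive comparison of the two groups from "self-report questionnaires completed by caregivers". Neither names the instruments in that sentence. The Clinical Study Description, however, counts "two behavioral assessments to note behavior occurring after sessions", and the Methods section describes two such instruments, the SDQ and the PANAS. It says that the PANAS is given weekly to capture effects in daily life outside sessions.

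For the SDQ, Methods names the person being rated: its scores give a "complete overview of the child's behavior during the past four weeks". For the PANAS, Methods gives the number of items, the scoring and the recall period of one week. It does not say who answers or whose affect is rated.

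The PANAS-SF form appended to the protocol has one instruction for all 20 items, "Indicate the extent you have felt this way over the past week", and ends with a line headed "Your scores on the PANAS".

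**The concern.** The plan's phrase does not fix the target of measurement. A caregiver's self-report describes the caregiver, and a caregiver's account of the child is not self-report. The form should resolve this, but it points to the respondent. Its items are single adjectives (guilty, proud, jittery and so on), so the one stem decides whose affect is scored.

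If the plan and form were followed as written, caregiver mood would be reported as the child's emotional regulation. Caregivers of nonverbal and verbal children may differ in their own affect for reasons unrelated to the therapy or to the child's regulation. A difference between the groups on these scores would then say nothing secure about the children. No later analysis can repair scores whose subject is unknown.

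**Working it through.** The plan gives no design figure on this point, so the check is mainly a comparison of the texts.

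1. **Is the PANAS among the caregiver-completed questionnaires?** The sentence does not name it. The Clinical Study Description counts two assessments of behavior after sessions, and Methods describes the SDQ and the PANAS. The IRB application lists further instruments, but Methods gives this role to these two only. The inference is strong, though it remains an inference.

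2. **Who is the intended target?** The child. Objective 3 concerns children, and the SAP's opening sentence attributes the out-of-session behavior to the participants.

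3. **Does the form match that target?** Not as printed. Both the stem and the score line address the person filling it in, and no wording for a child or proxy appears. The dog-behavior questionnaire in the same appendix, by contrast, tells its respondent to rate the dog.

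4. **Is the scoring itself sound?** Yes. The key assigns 10 items to each scale and uses items 1 to 20 once each. The range per scale is 10 × 1 = 10 to 10 × 5 = 50, as Methods and the form both state. The problem is whose affect is scored, not the arithmetic.

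5. **Which readings are possible?**
   - *Caregivers rated themselves.* This is what the plan and the form say when taken literally. The scores are then caregiver affect.
   - *Caregivers rated the child.* This best fits the intended target, but it needs an instruction or wording that is not shown.
   - *Children rated themselves.* This fits the second-person stem and the word self-report, but it contradicts the statement that caregivers completed the questionnaires. The IRB application explicitly assigns self-report to children for one measure only, the distress thermometer, and limits it to those aged 8 and older who are cognitively able.

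6. **How much of Objective 3 is touched?** The SDQ yields 5 domain scores plus total, impact, internalizing and externalizing: 5 + 4 = 9. The PANAS yields 2. The share is 2 / (9 + 2) = 2/11, or 18% of the score types described. This counts affected measures and does not estimate bias.

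**The case against.** The best defence is that caregivers rated the child. The SAP says the behavior of interest is the participants', and Methods says the PANAS captures therapeutic effects in daily life, and it is the child who receives the therapy. The appended page, with its scoring key, published means and citation, looks like a standard copy of the instrument and may not be the version caregivers saw. Any electronic version is not shown, and part of the document was removed before review, so a proxy instruction may exist.

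Most of this stands. It shows what the investigators intended, and it rules out treating the scores as proven caregiver mood. It does not show that the form carried out that intention. The IRB application's statement that caregivers enter survey data in REDCap helps only a little, because PANAS scores are listed separately, among data kept on a password-protected laptop.

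Two stronger readings are tempting. A reader might infer that the PANAS results are definitely caregiver affect; the documents do not support this, because the wording actually used is not shown. A reader might also infer that children answered and that nonverbal children could not do so validly. That reading contradicts the stated respondent and is the less likely one.

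**Conclusion.** The point holds as a mismatch between the stated respondent, the intended target and the form supplied. As documented, PANAS scores cannot be securely attributed to the child. If caregivers completed the form as printed, the result would be wrong for Objective 3, so this is more than a missing detail.

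The conclusion rests on two assumptions: that the PANAS is one of the caregiver-completed questionnaires, and that no proxy instruction exists in material not shown. If the second fails, a sentence documenting the instruction largely closes the matter.

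The reach is modest: a descriptive comparison on 2 of 11 score types, with no hypothesis test attached. A reader might extend the doubt to the SDQ, but its form is not shown and its description refers to the child. The t-tests use coded session behavior and do not depend on either questionnaire. The issue should be settled before PANAS results are reported under Objective 3.

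**What to change.** 1. Establish from the records who answered the PANAS, about whom, and with what wording or spoken instruction.
2. Unless a proxy instruction was given, label scores that caregivers gave to the printed stem as caregiver affect, or leave them out of the Objective 3 conclusion. Do not pool them with any scores that children gave.
3. For further use, reword the caregiver form's stem to ask about the child and label the result caregiver-rated child affect. State that the reliability figures in Methods (alphas of 0.86 to 0.90 for positive affect and 0.84 to 0.87 for negative affect) are not shown to apply to proxy ratings.
4. Replace the phrase "self-report questionnaires completed by caregivers" in both the Design section and the SAP with a description of what was done.

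The cost is a records check and a few wording changes. The downside is that some or all PANAS data may drop out of Objective 3, leaving the SDQ to carry it. A reworded stem cannot repair data already collected.
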